#### 4.3.3.2 Additional Measures

**COVID-19 Clinic Assessment.** Due to the current coronavirus pandemic, we anticipate that clinicians are experiencing changes to the format and volume of their clinics. Thus, we have added 13 items to the baseline survey assessing these changes including format (e.g., use of telehealth and availability of support staff), volume, and length of visits, and whether any of these changes may have had an impact on clinicians' ability or priority level regarding discussing sexual health with their patients. These items were drafted with the input of the multidisciplinary study team. Because these items were drafted after several clinicians had completed the study, these clinicians will be re-consented with a modified, abbreviated informed consent form and asked to complete only the COVID items.

## **5.0 Risks to Participants**

This study involves participation in qualitative interviews, or participation in a behavioral intervention study with minimally invasive assessments (i.e., self-report). The major risks for study subjects are (1) discomfort at answering study questions or during discussions with clinicians, (2) loss of privacy or confidentiality. Due to the protections we will have in place, we believe these risks to be minimal. There are no procedures that will be conducted as part of the study.

## **6.0 Potential Benefits to Participants**

There may be no direct benefit to the study participants. It is possible that the provider intervention will be effective at improving their knowledge, beliefs, and communication skills with respect to sexual health, and therefore have a beneficial effect on patient care or on patient-provider relationships, but this cannot be guaranteed. The research may inform future research to improve the quality of care given to patients with breast cancer. The minimal risks to subjects are reasonable in relation to potential benefit in improving clinicians' communication and clinical care of patients.

## **7.0 Provisions to Maintain the Confidentiality of Data**

In order to minimize the risks associated with discomfort in answering questions, participants will be told that they do not have to answer any research questions and that, if they change their mind about participating, they can stop at any time. All information collected for this study will be kept confidential. Subjects will be told that all information will be kept in strict confidence. All data will be stored on computer files or in locked filing cabinets to which only select members of the research staff will have access. All discussions about the study and training sessions will occur in private areas or over the telephone. In order to minimize the risks associated with loss of confidentiality, all will be kept confidential and secure, will be de-identified for analytic purposes, and none of the participants' information will be released to their employer or any other third party without the clinician's permission, except as required by law.

## **8.0 Costs to Participants**

There are no costs to participants for their participation in the study.

## **9.0 Consent Process**

Consent from participants will be obtained at the following time points: For the cognitive interviews, in-person immediately before the interview, in the location where the qualitative interview will be held, by the PI or other consent designee (clinicians may also consent online via REDCap link in advance of their interview); for the pilot study, electronic consent will be obtained through REDCap or, for clinicians who prefer paper and pencil consents, written consent will be obtained in person or through US Mail. Only Participants will be given time to ask questions privately before they sign consent forms. Only English speaking clinicians will be enrolled.

## **10.0 Off-Study Criteria**

Any participant may leave the study at any time due to distress or other reasons. We do not have a priori reasons for letting participants off the study.

## 11.0 Drugs and Devices

N/A

## 12.0 Multi-Site Research Study

N/A

## 13.0 Statistical Analysis

We plan to enroll 30-35 providers to the pilot study, in order to collect complete data from 30 study

completers; this sample size will be adequate to achieve the study objectives of testing the feasibility, acceptability, and preliminary effects of the iSHARE intervention. Descriptive analyses (e.g., frequencies, measures of central tendency) will determine the feasibility

and acceptability of the intervention. The operating characteristics of the feasibility/acceptability criteria under favorable and unfavorable characteristics are shown in **Table 3**. For example, if the true retention rate is high (80%), we will have a 94% chance of meeting the feasibility criteria of 70%, but if the true retention rate is low (55%), we will only have a 7% chance of falsely declaring feasibility.

**Table 3. Feasibility and Acceptability Determination**

Criterion	Decision rule	True favorable rate	True unfavorable rate	Probability correctly declaring feasibility	Probability incorrectly declaring feasibility
Enrollment	>40% ( $\geq 30/75$ approached)	50%	30%	97%	4%
Retention	$\geq 70\%$ ( $\geq 21/30$ enrolled)	80%	55%	94%	7%
Completion	$\geq 60\%$ ( $\geq 18/30$ enrolled)	70%	45%	92%	7%
Acceptability	$\geq 75\%$ ( $\geq 14/18$ endorsing)	85%	55%	88%	4%

**Feasibility** will be measured through study accrual, retention, and intervention completion. The following rates will be used as benchmarks for feasibility: Enrollment  $\geq 40\%$  of eligible candidates; retention  $\geq 70\%$ ; and intervention completion  $\geq 60\%$ . Although we achieved very high enrollment, retention, and completion rates in our previous pilot study, these estimates are lowered as we will be recruiting a larger sample of clinicians, many of whom will be from outside FCCC. **Acceptability** will be determined in two stages. First, at the individual level, we determine whether the individual met our acceptability criteria, which means endorsing 75% of the 6 primary acceptability items for both podcast episodes (12 items total; satisfaction, informativeness, relevance, ease of listening, likelihood to recommend, likelihood to impact practice) favorably ("Quite a bit"/"Very"). For participants who complete only one set of these items, as in the case that they listen only to podcast episode 1 and complete that survey but not the one after episode 2, we will consider 5/6 items rated favorably as meeting the threshold for acceptability. Second, if 75% of the sample (shown above at the minimal number needed to meet the completion benchmark, or 18) meets that definition, then we will be able to say that overall the study meets the standard set for acceptability.

Other data obtained from the acceptability surveys (e.g., length of time listened to each podcast, qualitative survey responses) will be analyzed descriptively or using thematic analysis as appropriate. Exploratory intervention usage data will be analyzed descriptively.

Prior to conducting analyses of outcome data, we will conduct analyses of internal reliability on the outcome measures. The sum of all items answered correctly will be used as the score for knowledge in analyses; if there are missing data on the item level, we may substitute percentage correct for the sum

of correct answers. For beliefs and communication behaviors, mean scores across all items on these scales will be used as the scores for these measures in analyses, assuming that the internal reliability for these measures is acceptable (Cronbach's alpha > .60). Otherwise, individual item scores may be used. We may also present data on individual items in an exploratory fashion to facilitate interpretation of findings. In line with recommendations for the analysis of data from pilot studies, preliminary outcome data will be analyzed descriptively, 95% confidence intervals will be calculated, and these data will be used to summarize the data at the three assessments.

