## 2.0 Objectives

The objective of the proposed study is to adapt a previously tested brief intervention aimed at enhancing clinicians' communication about sexual health (iSHARE) to a mobile web-based platform showcasing a two-part podcast and to assess the feasibility, acceptability, and preliminary effects of the intervention in breast cancer clinicians.

**Specific Aim 1.** To assess the feasibility and acceptability of iSHARE in a mLearning format.

**Hypothesis 1.** iSHARE will be judged as feasible, determined through measures of rates of participant enrollment, retention, and study completion.

**Hypothesis 2.** iSHARE will be judged as acceptable, determined through post-intervention evaluations of intervention satisfaction, helpfulness, and relevance, and ease of participation.

**Specific Aim 2.** To assess the preliminary effects of iSHARE in a mLearning format.

**Hypothesis 3.** iSHARE will show positive effects on clinicians' knowledge, beliefs (self-efficacy, outcome expectancies), and communication with respect to sexual health from pre-to post-intervention.

[figure not shown]

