
#### 4.3.2 Intervention

All participants will receive the iSHARE podcast intervention. This will consist of a two-part podcast series with expert guests. **Part 1 (Education)** will include information on rates, types, and causes of breast cancer patients’ problems related to sexual health, models of sexual response (function), current evidence-based approaches for addressing sexual concerns (e.g., information from recent key randomized controlled trials), and information about patient resources. **Part 2 (Skills)** will target basic clinician communication skills, with a major focus being teaching the stepped-care model of sexual health care known as PLISSIT (see **Figure 2**), and an emphasis on the first two steps in the model, i.e., Permission and Limited Information. The major behavioral targets for

communication skills training that will be emphasized are initiating a conversation about sexual health, asking effective questions to patients about sexual health or concerns, offering information about the impact of breast cancer treatment(s) on patients' sexual health, and initiating a referral for a patient, when appropriate. Key topics within patients' sexual health that will be discussed could include vaginal dryness and discomfort during sexual activity, sexual desire or interest, safety of sexual activity during treatments, and body image or appearance. Information from the most updated NCCN Survivorship Guidelines, which provide guidelines for assessing and managing sexual function for cancer survivors, may also be included such as suggested wording for initial questions for clinicians to ask patients. Content could also include recognition of common patient and clinician barriers to effective communication about sexual health, patient preferences for communication about this topic, and discussion of contextual/socio-cultural factors, such as the partner's presence in the room, a gender mismatch between the patient and clinician, patient sexual minority status, or ethnic or religious differences. Other relevant information may also be added during the refinement phase.

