**Table 2. Pilot Self-Report Measures**

Measure	# Items	Minutes to Complete	Baseline	Post-Episode 1	Post-Episode 2
Demographics	6	3	X	-	-
Knowledge	T1: 10 Post Ep 1: 5 T2: 5	3	X	X	X
Self-efficacy (Beliefs) 	3	1	X	-	X
Outcome Expectancies (Beliefs) 	7	3	X	-	X
Communication Behaviors	10	5	X	-	X
COVID-19 Clinic Assessment	13	5	X	-	-
Program Evaluation	12	5	-	X	X

Totals						
-	Baseline (T1)	49	20			
-	Post-Episode 1	17	8			
-	Post-Training (T2)	37	17			

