**Aim 2.** Preliminary effects of the iSHARE intervention will be assessed using self-report surveys at three time points (Pre-intervention, Post-episode 1, and Post-episode 2) and will assess clinicians' knowledge, beliefs (self-efficacy, outcome expectancies), and communication about sexual health (See Table 2). In accordance with current recommendations to include specific communication behaviors as outcomes in communication training trials and with findings of recent reviews on outcomes with proven sensitivity to communication interventions including our own iSHARE pilot project, the *key outcomes* will be clinicians' self-reported (1) **knowledge** across three major areas (sexual response/breast cancer-related sexual side effects, common approaches and resources for these problems, and basic communication skills pertaining to sexual health), assessed through 10 true/false or multiple-choice items developed for this study that were adapted from items used in similar research by the study team and found to be sensitive to communication interventions, (2) two aspects of clinicians' **beliefs**, assessed using items developed for the initial iSHARE study based on social cognitive theory, that showed sensitivity in the pilot project and are rated on a 0-10 point scale where 0=not at all confident or do not agree at all and 10=extremely confident or very strongly agree, namely (a) self-efficacy for communicating with breast cancer patients about sexual health (3 items; Cronbach's alpha in pilot =.77), and (b) outcome expectancies for communicating with breast cancer patients about sexual concerns (7 items; Cronbach's alpha in pilot =.90), and (3) **communication behaviors**, assessed using two sets of items, (a) clinicians' perceived comfort in engaging in key communication tasks (e.g., asking the patient if she has any sexual concerns, discussing the patient's loss of sexual interest or desire; 7 items), and (b) items adapted from those published in a similar trial and captures the frequency of engaging in three key types of communication about sexual health with breast cancer patients (e.g., initiating a conversation about sexual health, offering information about the impact of breast cancer treatment(s) on sexual health; 3 items), rated on a 1 to 5 scale where 1=never/almost never and 5=always/almost always.

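### Section 13.0 does not name within-person change as the Hypothesis 3 estimate, and knowledge sums taken survey by survey rest on 10, 5 and 5 items

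*Combined protocol and SAP*

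**What the plan says.** Section 2.0 (Hypothesis 3) expects positive effects on clinicians' knowledge, beliefs and "communication with respect to sexual health from pre-to post-intervention". Section 4.3.2 makes this a single-arm study: "All participants will receive the iSHARE podcast intervention".

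Section 13.0 gives the outcome analysis in one sentence. Preliminary outcome data are to be treated descriptively, "95% confidence intervals will be calculated, and these data will be used to summarize the data at the three assessments". No change score, paired interval or repeated-measures method is named. On numbers, the section says "We plan to enroll 30-35 providers to the pilot study, in order to collect complete data from 30 study" completers, but it does not formally name an analysis set for Aim 2.

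For knowledge, Section 4.3.3.1 describes one measure, "assessed through 10 true/false or multiple-choice items developed for this study". The knowledge row of Table 2 reads "T1: 10 Post Ep 1: 5 T2: 5". Section 13.0 sets the score: "The sum of all items answered correctly will be used as the score for knowledge in analyses". It offers one alternative: "if there are missing data on the item level, we may substitute percentage correct for the sum".

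Table 2 places self-efficacy, outcome expectancies and communication at baseline and post-episode 2 only. Knowledge is the only one of these outcomes measured at all three surveys.

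**The concern.** With no control arm, the only effect that Aim 2 can estimate is the change within the same clinicians. A reader will want its size and its uncertainty. The uncertainty of a change depends on the correlation between the two measurements, and a table of means with intervals at each survey does not carry that information. If the report follows the Section 13.0 sentence at its most literal, the central quantity of Hypothesis 3 cannot be recovered from it.

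The knowledge score raises a second, separate question. A count of correct answers out of 10 cannot be set beside a count out of 5. Reported survey by survey, the first-listed key outcome could show a loss when knowledge is unchanged or better. Percentage correct would remove the difference in length, but the plan allows it only where item data are missing.

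**Working it through.** **Is the 10/5/5 split real?** Adding the item counts in Table 2 reproduces its stated totals:
- Baseline: 6 + 10 + 3 + 7 + 10 + 13 = 49 (stated 49).
- Post-episode 1: 5 + 12 = 17 (stated 17).
- Post-episode 2: 5 + 3 + 7 + 10 + 12 = 37 (stated 37).

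The split is therefore intended and is not an artefact of a broken table.

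**Change compared with per-assessment intervals.** Inputs: n = 30 (planned completers, Sections 4.1 and 13.0) and the 95% level (Section 13.0). The documents give no SD and no pre-post correlation for the outcomes. Equal SDs are assumed, and the correlation ρ is shown as a range.

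- Per-assessment half-width = t(0.975, 29)/√30 = 0.373 SD, whatever ρ is.
- Paired-change half-width = t(0.975, 29) × √(2(1 − ρ))/√30, that is, 0.373 × √(2(1 − ρ)):

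| Assumed ρ | √(2(1 − ρ)) | Half-width for change (SD) |
|---|---|---|
| 0.3 | 1.183 | 0.442 |
| 0.5 | 1.000 | 0.373 |
| 0.7 | 0.775 | 0.289 |
| 0.8 | 0.632 | 0.236 |

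Treating the two time points as independent samples gives t(0.975, 58) × √(2/30) = 0.517 SD, wider than every row above.

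As an illustration, take an observed mean gain of 0.33 SD. Its interval is 0.33 ± 0.442, or −0.11 to 0.77, at ρ = 0.3. At ρ = 0.8 it is 0.33 ± 0.236, or 0.09 to 0.57. The per-assessment means and intervals are identical in the two cases.

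**Knowledge sums.** Percent-correct values are assumed for illustration.

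| Percent correct, before → after | Baseline sum (of 10) | Post-ep. 1 sum (of 5) | Post-ep. 2 sum (of 5) | Two later sets combined (of 10) |
|---|---|---|---|---|
| 60% → 60% | 6 | 3 | 3 | 6 |
| 60% → 80% | 6 | 4 | 4 | 8 |
| 50% → 100% | 5 | 5 | 5 | 10 |

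Survey by survey, no change looks like a loss of 3, a rise to 80% looks like a loss of 2, and a rise from half right to all right looks like no change. Because a later sum cannot exceed 5, any baseline sum above 5 must fall. Combined into one 10-item post score, the same three cases show 0, +2 and +5. That comparison is valid only if the later items repeat the baseline ten.

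**The case against.** The case for leaving the text alone has real weight.

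- **Change is not ruled out.** A reader might infer that the plan omits an analysis of change. The text does not support that. The clause on confidence intervals has no object, and the mention of three assessments cannot be literal for beliefs and communication, which are measured twice. It is a loose sentence, not a restriction. What stands is that the estimate is not named.
- **Knowledge may be comparable.** A reader might also infer that the knowledge score cannot be compared over time, or that it will show a fall. Neither follows. Section 4.3.3.1 describes one 10-item measure, and 5 + 5 = 10, so the natural reading is that the two later quizzes together repeat it. On that reading the total number correct runs from 0 to 10 both before and after. Even survey by survey, a fall is forced only when the baseline sum exceeds 5; a rise from 40% to 100% gives 4 to 5. The survey forms, listed as appendices in Section 19.0 but not in the available text, may settle whether the items repeat. What stands is that no rule in that text says they repeat or how to combine them.
- **The analysis set is nearly clear.** Section 4.1 recruits until 30 clinicians complete the study, and Section 4.3.3.1 defines retention as completing every survey. Both point to completers, though no Aim 2 set is stated.
- **It is a pilot.** Descriptive analysis is appropriate, and no decision rule depends on Hypothesis 3. The absence of a significance test or power calculation is not a fault. A mean change with its interval is itself descriptive.

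**Conclusion.** The point holds as a gap in specification, in two parts.

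First, Section 13.0 does not name the within-person change as the Aim 2 estimate, and per-assessment summaries alone cannot give its uncertainty. With 30 pairs, the half-width for change lies between 0.44 and 0.24 SD for correlations of 0.3 to 0.8, against a fixed 0.37 SD at each assessment. This rests on equal SDs and on correlations that the documents do not give.

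Second, knowledge sums reported survey by survey are not on one scale (maximum 10, then 5, then 5). This affects knowledge only; beliefs and communication are mean scores on the same scales at both of their assessments. The percent-correct figures are illustrations, but the ceiling of 5 is arithmetic.

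The paired data will be collected in any case, and no feasibility or acceptability criterion is touched. This is a free improvement, not a threat to the study's conclusions.

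**What to change.** In Section 13.0:

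1. State that the Aim 2 estimate for self-efficacy, outcome expectancies, communication comfort and communication frequency is the mean within-person change, post-episode 2 minus baseline. Report it with a paired 95% confidence interval and the number of pairs, among participants with both measurements. Comfort (7 items) and frequency (3 items) are named separately because Section 4.3.3.1 defines them as two item sets.
2. For knowledge, do not compare raw sums across surveys of different length, and state which of these cases applies:
   - if the later items repeat the baseline ten, combine the two 5-item sets into one 10-item post score and report its paired change from baseline with a 95% interval;
   - if only some items repeat, compare the repeated items only;
   - if the later items are new, report percentage correct per survey and say that the item content differs.
3. Keep the per-assessment summaries as description.

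A comparison of completers with non-completers is not needed. Section 4.1 expects 33 consented for 30 completers, so it would rest on about 3 people.

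The cost is three or four sentences of analysis wording. No new data, hypothesis test or decision rule is involved.

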#### **14.0 Data Safety Monitoring Plan**

The PI will take responsibility for monitoring the safety of all phases of the research study. Because of the nature of the research as involving procedures without significant risk (e.g., surveys; listening to audio podcasts) there are unlikely to be any adverse events. Study staff will report any adverse events they observe to the PI within 24 hours. The consent form will contain the contact information for the PI and the Institutional Review Board (IRB), and state that participant may contact her or the IRB at any time. A DSMB is not required for the current study.

#### **15.0 Adverse Events**

Because of the nature of the research as involving procedures without significant risk (e.g., qualitative interviews; surveys; listening to an audio podcast) there are unlikely to be any serious adverse events and adverse events are likely to be rare. Possible risks include feeling worried, anxious, or concerned during questionnaire completion, during the cognitive interview, or while listening to the podcast. All participants are informed of possible adverse psychological reactions associated with participating in the study during the informed consent process.

Any unexpected or adverse event that occurs during data collection or study procedures is reported immediately to the Principal Investigator, who is responsible for documenting all adverse events with the FCCC IRB within 24 hours. For participants who are experiencing psychological distress reactions, the study team member or research assistant alerts the Principal Investigator, who would provide the participant with a referral to appropriate services. At FCCC counselors in the Department of Social Work are trained to provide psychological support services or to make specific referrals to other psychological counseling or psychiatric services in the area as needed.

The research team will keep a log tracking the number, nature, and frequency of adverse events as part of each phase of the research plan. In accordance with FCCC guidelines, this protocol will employ the following mechanisms for adverse event reporting: 1) alert the FCCC review committees of any and all reports of adverse events; 2) inform all members of the study team of any all reports of adverse events. If 3 or more adverse events are reported, the study team will assess potential causes of the adverse events and, if events are clearly linked to study participation, discontinue the study.

